18. APPENDICES

18.1. Modified International Working Group AML Response Criteria

Hematologic Response According to IWG Criteria for AML is reported in table [Table 4](#).

Table 4: Hematologic Response According to IWG Criteria for AML

Category	Definition
Morphologic Complete Remission (CR)	The following conditions should be met: 
 • Absolute neutrophil count (ANC) > 1000/uL and platelets > 100,000/uL without transfusions and/or exogenous growth factor support (ie, no transfusion or exogenous growth factor within 7 days of assessment). • Bone marrow with < 5% blasts and evidence of trilineage hematopoiesis. • No evidence of extramedullary disease.
Morphologic Complete Remission With Incomplete Blood Count Recovery (CRi)	
 • ANC < 1000/uL. • Platelets < 100,000/uL or > 100,000/uL without platelet recovery (requiring transfusion within 7 days of assessment). • Bone marrow with < 5% blasts and evidence of trilineage hematopoiesis. • No evidence of extramedullary disease.
Partial Remission (PR) ^a	
 • ANC > 1000/uL and platelets > 100,000/uL without transfusions and/or exogenous growth factor support (ie, no transfusion or exogenous growth factor within 7 days of assessment). • Bone marrow with 5% to 25% blasts and at least a 50% decrease in bone marrow blast percent from baseline. • No evidence of extramedullary disease.
Treatment Failure	Resistant Disease: Patient survives ≥ 7 days post-therapy and failed to achieve CR, CRi, or PR but are stable with persistent AML in blood or bone marrow.

Category	Definition
	
Aplasia: Patient survives ≥ 7 days post-therapy; death while cytopenic, with aplastic bone marrow.
 
Indeterminate cause:
 
 • Patients who die < 7 days post-therapy. • Patients who die > 7 days post-therapy with no peripheral blood blasts, but no bone marrow examination. • Patients who do not complete the first course of therapy. 
Morphologic relapse after CR or CRi:
 
 • the reappearance of $> 5\%$ blasts in the peripheral blood, or • a single finding of $> 15\%$ blasts in the bone marrow. 
All of the above occurrences should be attributed to relapse following CR or CRi and not attributable to another cause (eg, bone marrow regeneration after consolidation therapy).
 
Molecular or cytogenetic relapse: Reappearance of molecular or cytogenetic abnormality.

^a If the pretreatment bone marrow blast percentage was 50% to 100%, the percentage of blasts must decrease to a value between 5% and 25%; if the pretreatment blast percentage was 20% to less than 49%, they must decrease by at least half to a value of more than 5%.
 Source: [Cheson, 2003](#).

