Appendix D: Modified International Working Group AML Response Criteria

Hematologic Response According to IWG Criteria for AML	
Category	Definition
Morphologic Complete Remission (CR)	
The following conditions should be met:
 
 • Absolute neutrophil count (ANC) \geq 1000/μL and platelets \geq100,000/μL without transfusions and/or exogenous growth factor support (ie, no transfusion or exogenous growth factor within 7 days of assessment). • Bone marrow with < 5% blasts and evidence of trilineage hematopoiesis. • No evidence of extramedullary disease.
Morphologic Complete Remission With Incomplete Blood Count Recovery (CRi)	
 • ANC < 1000/μL. • Platelets < 100,000/μL or > 100,000/μL without platelet recovery (requiring transfusion within 7 days of assessment). • Bone marrow with < 5% blasts and evidence of trilineage hematopoiesis. • No evidence of extramedullary disease.
Partial Remission (PR)^a	
 • ANC \geq 1000/μL and platelets \geq 100,000/μL without transfusions and/or exogenous growth factor support (ie, no transfusion or exogenous growth factor within 7 days of assessment). • Bone marrow with 5% to 25% blasts and at least a 50% decrease in bone marrow blast percent from baseline. • No evidence of extramedullary disease.

Hematologic Response According to IWG Criteria for AML	
Category	Definition
Treatment Failure	
Resistant Disease: Patient survives ≥ 7 days post-therapy and failed to achieve CR, CRi, or PR with persistent AML in blood or bone marrow.
 
Aplasia: Patient survives ≥ 7 days post-therapy; death while cytopenic, with aplastic bone marrow.
 
Indeterminate cause:
 
 • Patients who die < 7 days post-therapy. • Patients who die > 7 days post-therapy with no peripheral blood blasts, but no bone marrow examination. • Patients who do not complete the first course of therapy. 
Morphologic relapse after CR or CRi:
 
 • the reappearance of $> 5\%$ blasts in the peripheral blood, or • a single finding of $> 15\%$ blasts in the bone marrow. 
All of the above occurrences should be attributed to relapse following CR or CRi and not attributable to another cause (eg, bone marrow regeneration after consolidation therapy).
 
Molecular or cytogenetic relapse: Reappearance of molecular or cytogenetic abnormality.

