1. JUSTIFICATION FOR AMENDMENT

Significant changes included in this amendment are summarized below:

- Removed progressive disease as part of the response criteria to avoid confusion with the overlapping definition of treatment failure. Progressive disease adds no utility in addition to treatment failure in the criteria. Language was updated throughout the document to align with the modified response criteria, including the use of the term 'relapse' and the deletion of 'resistant disease' (Protocol Summary, Table 2, Sections 4.1, 4.4, 6.20.1, 6.20.3, 6.20.4, 8.2, 8.2.1, 10.2, 10.6.2, 10.8, 12.1, Appendix D and G).
- Clarified that if clinically inappropriate per the treatment site, a subject may have the bone marrow evaluation omitted at treatment discontinuation if peripheral blast results are collected (Table 2 and 6.22).
- Clarified that subjects demonstrating clinical benefit as per the Investigator at the end of Cycle 4 and beyond may continue to receive lenalidomide on study for up to 12 cycles in the absence of protocol-defined toxicity, or transitioning to allogeneic HSCT (Protocol Summary, Sections 4.1, 4.4, 6.20.1). Clarified that subjects who do not demonstrate clinical benefit as per the Investigator at the end of Cycle 4 and beyond will be discontinued from lenalidomide treatment (Section 8.2.1).
- Updated the ALT/AST inclusion criteria by providing a specific upper limit of normal (ULN), as well as updated ULN for ALT/AST when considering dose reduction/interruption and AE grading (Sections 7.2, 8.2.1, 11.2.2).

The amendment also includes typographical and formatting corrections, and several other minor clarifications and corrections, including:

- The brand name of REVLIMID was capitalized throughout the document to maintain consistency (Protocol Summary, Sections 6.25 and 18).
- Updated the word 'relapse' to 'relapsed' throughout the document (Section 1.4.2 and Table 2)
- Added '(with second or greater relapse or refractory to at least 2 prior induction attempts)' as part of the primary objective to align with Section 2 (Section 1.4.2).
- Amended wording from 'summaries' to 'summarized' under Molecular and Cellular Measurements (Section 10.8).

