10.2.2. Overall Response Rate

Overall response rate defined as the proportion of subjects with best response (CR, CRi or PR) among all subjects in the ITT population (i.e. subject will be considered as having a response if they achieve at least PR). Subject achieving less than PR (i.e. 'treatment failure') or having no assessment will be considered as a non-responder. If a subject is missing some assessments, their best response from available assessments will be selected as the response. Responses occurring after a treatment failure will not be considered. All assessments collected while a subject is under study treatment (incorporating, wherever applicable, the 28 day rule, i.e. last dose plus 28 days) will be considered.

The ORR formula will be the following

$$\text{ORR} = (\text{number of CR, CRi or PR from start to the end of period under analysis}) / (\text{number of subjects within the ITT population}).$$

The ORR rate at the end of Cycles 1, 2, 3, 4, 8 and 12 will be categorized, and the rate will be calculated for each cycle dividing the number of subjects with response in the cycle by the number of subjects entering the cycle. The formula will be the following

$$\text{ORR cycle}_i = (\text{number of CR, CRi or PR from start of Cycle } i \text{ to the end of Cycle } i) / (\text{number of subjects entering Cycle } i \text{ within the ITT population}).$$

Proportions will be presented as percentages with frequency counts together with the Clopper-Pearson 95% CI, at the end of each pre-specified cycle.

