10.2.3. Disease Assessment Outcome

Disease assessment outcome (DAO) at the end of Cycles 1, 2, 3, 4, 8 and 12 of lenalidomide administration shall be categorized according to the Cheson criteria (Cheson, 2003, see Section 18.1) into the following categories: CR, CRi, PR, Treatment Failure (Resistant Disease, Aplasia, Indeterminate Cause, Relapse after CR or CRi, Molecular or Cytogenetic relapse), Missing/not done. Responses occurring after a treatment failure will not be considered. The DAO rate for each of the response criteria will be calculated as the total number of subjects in a given response category at each time point over the number of subjects entering each corresponding cycle. The formula will be the following:

DAO category cycle_i = (number of subjects with DAO category from start of Cycle i Day 1 to the end of Cycle i) / (number of subjects entering Cycle i within the ITT population)*100.

Proportions will be presented as percentages with frequency counts together with the Clopper-Pearson 95% CI, per response category at the end of each pre-specified cycle.

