15. PRIMARY AND END OF STUDY FINAL ANALYSES

All tables, listings and figures detailed in this SAP will be provided for the primary final analysis that will be conducted when all on treatment subjects will have completed their Cycle 4 Day 28 assessments or will have met discontinuation criteria, whichever occurs first.

For the end of study final analysis, all outputs will be rerun once all subjects will have discontinued the follow-up period (up to 5 years after the last subject first dose of lenalidomide).

16. Changes to the Statistical Analyses Section of the Protocol

Denominator of the ORR rate will be defined as the number of subjects starting the cycle of interest instead of the number of subjects completing the cycle of interest as stated in the protocol.

Correlation will be computed between response and laboratory results obtained at baseline, instead of correlation between response and laboratory results at diagnosis and relapse as stated in the protocol.

The IWG response criteria in this study was brought in line with the actual criteria, ie. 'Progressive Disease' was replaced with 'Treatment Failure'.

Time to response endpoint was added as a secondary endpoint.

During the course of the study, due to a low (1 or fewer) number of subjects reporting certain measurements or to redundant presentation, it was determined that the analyses listed below would not be conducted:

- Summaries of prior cancer history, prior procedures/surgeries, procedures for prior cancers not under study and radiation treatment for prior cancers not under study.
- [REDACTED]
- Correlation between response with baseline/screening peripheral white blood cell count, absolute blast count, cytogenetics, [REDACTED]
- [REDACTED]
- Summary of durable response rate.
- AE summary tables for (treatment-emergent adverse events leading to death, SAEs related to lenalidomide, SAEs leading to discontinuation, Grade $\frac{3}{4}$ TEAEs by maximum intensity.
- Summary for AE of special interest related to lenalidomide, SAEs of special interest related to lenalidomide or leading to discontinuation of lenalidomide. AEs of special interest by maximum intensity.
- Second primary malignancy related tables, listings and figures.
- [REDACTED]
- Population PK analysis.

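### SAP Table 4 limits resistant disease to stable subjects, so a surviving child who finishes the first course, never reaches CR/CRi and progresses has no treatment-failure sub-category

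*SAP*

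**What the plan says.** Protocol Appendix D classes as resistant disease a patient who survives at least 7 days post-therapy and "failed to achieve CR, CRi, or PR with persistent AML in blood or bone marrow". SAP 18.1, Table 4 gives the same entry with a condition added: "failed to achieve CR, CRi, or PR but are stable with persistent AML in blood or bone marrow".

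SAP 10.2.3 reports the disease assessment outcome by cycle, refers to SAP 18.1 for the criteria, and uses a closed list: "CR, CRi, PR, Treatment Failure (Resistant Disease, Aplasia, Indeterminate Cause, Relapse after CR or CRi, Molecular or Cytogenetic relapse), Missing/not done". Each category gets a rate and a Clopper-Pearson interval. Disease assessment outcome is a secondary endpoint (Protocol 3.2, SAP 4.2.2) and one of the interim outputs (SAP 14).

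Progressive disease is absent from the current criteria in both documents. The protocol's amendment summary explains the removal: "Progressive disease adds no utility in addition to treatment failure in the criteria". SAP 16 says only that progressive disease was replaced by treatment failure; it does not mention the stability condition.

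SAP 10.2.2 states the top-level rule for ORR: "Subject achieving less than PR (i.e. 'treatment failure') or having no assessment will be considered as a non-responder". SAP 10.1 adds, for the primary endpoint, that responses after a treatment-failure assessment are not considered.

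**The concern.** Once progressive disease was folded into treatment failure, the treatment-failure entries had to cover everyone who had been called progressive. Appendix D does this for children who never respond, because its resistant-disease entry takes in any persistent AML without CR, CRi or PR. Table 4 does not, because its added condition excludes the child whose disease is growing.

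For that child a programmer following Table 4 has two options. One is a sub-category whose definition the child does not meet. The other is the missing/not-done cell, for a child who was in fact assessed. The resulting sub-category rates would depend on an unwritten choice. The same labels also feed the SAP 10.1 rule that discards later responses, so an unclear treatment-failure label can reach the primary endpoint.

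**Working it through.** **1. The design figures.** Inputs from SAP 4.4 and Protocol 10.3: 18 subjects in Stage 1, continue with at least 3 responses; 43 in total, active with at least 8; p0 = 0.10, p1 = 0.25. With X the Stage 1 responses,

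P(active | p) = Σ over x = 3 to 18 of P(X = x; 18, p) × P(Bin(25, p) ≥ 8 − x).

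- At p = 0.10 this is 0.0480; at p = 0.25 it is 0.8003. The stated 5% and 80% reproduce.
- The probability of stopping after Stage 1 at p = 0.10 is 0.734, so the expected sample size is 18 + 0.266 × 25 = 24.7.

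Only CR and CRi enter these counts. A child who never responds is a non-responder under either definition of resistant disease.

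**2. The child in question, set against each Table 4 entry.** Take a child who completes the first course, survives at least 7 days, never reaches CR/CRi and has rising blasts.

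- Resistant disease: fails the stability condition in the SAP. Under Appendix D, a child with no PR either would qualify.
- Aplasia: requires death while cytopenic.
- Indeterminate cause: the entries cover certain deaths and "Patients who do not complete the first course of therapy"; neither applies.
- Morphologic relapse: requires an earlier CR or CRi.
- Molecular or cytogenetic relapse: requires an abnormality to reappear; none has gone away.

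No sub-category is left, and SAP 10.2.3 has no entry for other outcomes.

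**3. Progressing children who do have a place.** A child who progresses after CR/CRi is a relapse. A child who stops before completing the first course is indeterminate cause.

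**4. A related gap.** A child who reaches PR and then progresses has achieved PR, so the literal resistant-disease entry does not cover that child even in Appendix D. Deleting the stability words alone does not close this case.

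**5. Link to the primary endpoint.** Compare two children, both with persistent AML at Cycle 1 and CR at Cycle 3. If blasts were stable at Cycle 1, Table 4 makes that assessment treatment failure and SAP 10.1 discards the CR. If blasts were rising, Table 4 supplies no treatment-failure entry and the CR could count. If the below-PR rule of SAP 10.2.2 is carried over to SAP 10.1, both are discarded. Protocol 10.6.1 counts a CR/CRi at the end of Cycle 1, 2, 3 or 4 and has no discard rule, so there both count. SAP 16 does not list the discard rule as a change.

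**6. Why step 5 matters (illustration only).** Let f be the share of true responders whose CR/CRi is discarded because of an earlier resistant-disease assessment. The documents give no value for f. Putting 0.25 × (1 − f) into the formula of step 1:

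- f = 0.05: rate 0.2375, power 0.753
- f = 0.10: rate 0.225, power 0.697
- f = 0.20: rate 0.200, power 0.564
- f = 0.30: rate 0.175, power 0.411

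This loss comes from the discard rule. It does not measure the effect of the stability wording.

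**The case against.** The strongest reply is that the SAP already says where a progressing child belongs. SAP 10.2.2 equates anything below PR with treatment failure, and SAP 16 says progressive disease became treatment failure. Only the sub-label is open, and an assessed child is plainly not missing. This stands, and it confines the point to the sub-category rates.

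Second, for the primary endpoint SAP 10.1 takes responses as assessed locally and recorded on the response-assessment eCRF page, and sites work from the protocol, whose Appendix D has no stability condition. The SAP describes no step that re-derives resistant disease from blast counts. This also stands as a limit on practical harm, although Table 4 would then misdescribe the data it is meant to define. The eCRF itself is not among the documents.

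A reader might infer more than this, in three ways that the documents do not support:

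- That any living child whose AML progresses is unclassifiable. Relapse after CR/CRi and an incomplete first course both have entries.
- That the RR population changes. SAP 5.3.2 takes its treatment-failure clause from the treatment disposition eCRF page, and an assessed child qualifies anyway through having an IWG assessment.
- That the overall treatment-failure rate is understated by a computable amount. At the design rates 75% to 90% of 43 (32 to 39 subjects) would lack CR/CRi, but that group includes PRs, deaths and incomplete first courses. No document gives the share who progress. The planned rates also use subjects entering each cycle as denominator, not 43.

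**Conclusion.** The point holds in a limited form. SAP Table 4 departs from Protocol Appendix D without declaring it, and on a literal reading it leaves surviving children who complete the first course, never reach CR/CRi and progress without a treatment-failure sub-category. The consequence falls on the sub-category rates of a secondary endpoint that is also produced at the interim. ORR, RR membership and the responder status of children who never respond do not change, and the design figures reproduce. No size of effect can be derived: it depends on how many such children there are and on how sites and programmers label them, and the documents give neither. The conclusion assumes that Table 4 is applied as written.

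The discard rule in SAP 10.1 is the reason not to treat this as a purely editorial correction. Widening resistant disease to match the protocol, without touching that rule, would bring more early assessments under it.

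**What to change.** - In SAP 18.1, Table 4, delete the stability condition so that the entry matches Appendix D.
- In SAP 10.2.3, state that every assessed subject below PR is treatment failure, and that persistent AML with no prior CR/CRi is scored as resistant disease. This also covers progression after a PR.
- In SAP 10.1, reconcile the discard rule with the primary endpoint in Protocol 10.6.1, so that an early resistant-disease assessment does not remove a CR/CRi observed later within the 4 cycles. The same discard sentence stands in SAP 10.2.2 and 10.2.3 and should be made consistent with whatever is decided.
- Record the reconciled response rule in SAP 16 wherever it still differs from the protocol.
- The Treatment Phase text of SAP 4.1 still names resistant disease beside clinical benefit as a basis for entering the extension phase, while the current protocol names clinical benefit only. These passages must be reconciled.

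The cost is a few sentences in the SAP and a check of the response-derivation program. No new data, visits or subjects are needed.

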18.2. Pharmacokinetic Sample Collection

18.2.1. Blood Collection for PK Analysis

Collection of blood samples for PK assessments in plasma will be performed in all subjects. On Cycle 1 Day 1, the subjects will receive the dose of lenalidomide in the morning at the study center. Subjects will undergo PK sampling of blood at scheduled time points (Table 5) for 24 hours post-dose. The actual date and time for dosing and blood sampling should be recorded in the eCRF.

Table 5: PK Sampling Schedule During Cycle 1 Day 1

Collection time after lenalidomide administration ^a	Collection window	Weight ≤ 20 kg ^b	Weight > 20 kg ^c
0.5 hour	± 10 min	-	x
1 hour	± 10 min	x	x
2 hours	± 10 min	x	x
4 hours	± 10 min	x	x
6 hours	± 10 min	-	x
8 hours	± 10 min	x	x
24 hours*	± 2 hours	x	x

PK = pharmacokinetic.

* The 24 hour blood sample must be taken prior to the lenalidomide administration on Day 2.

^a The blood draw volume is 1 mL per sample.

^b Only 5 PK blood samples will be taken from subjects with weight ≤ 20 kg at the specified time points.

^c Seven PK blood samples will be taken from subjects with weight > 20 kg.

18.3. Handling of Dates

Dates will be stored as numeric variables in the SAS analysis files and reported in DDMMYYYY format (i.e., the Date9. date format in SAS). Dates in the clinical database are classified into the categories of procedure dates, log dates, milestone dates, outcome dates, and special dates.

- **Procedure Dates** are the dates on which given protocol-specified procedure are performed. They include the dates of laboratory testing, physical examinations, tumor scans, etc. They should be present whenever data for a protocol-specified procedure are present and should only be missing when a procedure are marked as NOT DONE in the database. Procedure dates will not be imputed.
- **Log Dates** are dates recorded in eCRF data logs. Specifically, they are the start and end dates for adverse events and concomitant medications/procedures. They should not be missing unless an event or medication is marked as *ongoing* in the database. In listings, log dates will be shown as recorded without imputation.
- **Milestone Dates** are dates of protocol milestones such as randomization, study drug start date, study drug termination date, study closure date, etc. They should not be missing if the milestone occurs for a subject. They will not be imputed.
- **Outcome Dates** are dates corresponding to study endpoints such as survival, treatment failure, etc. In most cases they are derived either from a milestone (eg, the survival date is derived from the death date), or a procedure date (eg, the treatment failure date is derived from the date of the tumor scan that was used to determine treatment failure). They may be subject to endpoint-specific censoring rules if the outcome did not occur, but are not otherwise subject to imputation.
- **Special Dates** cannot be classified in any of the above categories and they include the date of birth. They may be subject to variable-specific censoring and imputation rules.
- **Last Contact Dates** for the survival analysis are the maximum date collected in the database. If the imputed date used for response date or AE date, the last contact dates should be the latest date of those imputed date and maximum date in the database.

Dates recorded in comment fields will not be imputed or reported in any specific format.

